1.1 Overview of thyroid cancer

Thyroid cancer is the most common endocrine cancer worldwide representing approximately 1% of all cancers and responsible for 0.5% of all cancer related deaths. The worldwide incidence of thyroid cancers has however, increased significantly in the last 2 decades with a near doubling of the incidence rate.¹⁻⁵ A review of the US population cancer surveillance database showed that the incidence of thyroid cancer increased from 3.6 per 100,000 in 1973 to 8.7 per 100,000 in 2002.⁵ This increase cuts across racial groups with a 150% in the US Caucasian population and a 73% increase in African Americans.⁶ Approximately 40,000 new cases of thyroid cancers were diagnosed in the US in 2008. Whereas a large majority of patients with thyroid cancers present with localized disease and therefore achieve disease control with surgical resection, there is a substantial rate of disease relapse in up to a third of patients. Half of such relapses occur at distant sites with mortality approaching 50% at 5 years with currently available systemic treatment options. Radioactive iodine has been the mainstay of systemic therapy for metastatic differentiated thyroid cancers.⁷ However, alternative treatment options are warranted due to the limitations imposed by radiation exposure limits, and the histologic progression with loss of differentiation and impaired uptake of radioiodine which can occur in up to 70% of patients with original diagnosis of papillary thyroid carcinoma. The use of biologic agents targeting cellular pathways in thyroid cancer has shown some promise. Multi-targeted tyrosine kinase inhibitors such as sorafenib, sunitinib, axitinib and motesanib have produced encouraging clinical benefit with objective responses (mainly partial responses) observed in approximately 15 - 30% of patients with iodine refractory disease. Majority of the patients experienced disease stabilization with a median progression free survival ranging between 40 and 80 weeks.⁸⁻¹⁰

Medullary thyroid Cancer: Vandetanib is a multi-targeted tyrosine kinase inhibitor with predominant activity against EGFR and VEGFR kinase enzyme activity. This drug received approval from the U. S. Food and Drug Administration for the treatment of symptomatic or progressive locally advanced, or metastatic medullary thyroid cancer patients. The drug was evaluated in an international, multicenter, double-blind trial that randomized MTC patients in a 2:1 ratio to receive either Vandetanib or placebo. The study met its primary objective of a PFS improvement in patients treated with Vandetanib (HR=0.35; 95% CI: 0.24, 0.53; p<0.0001). At the primary PFS analysis, 15% of the patients had died and no significant OS difference was noted. The overall response rate was 44% versus 1% in favor of patients randomized to receive Vandetanib.

The most common adverse events included diarrhea/colitis, rash, dermatitis acneiform, nausea, hypertension, headache, fatigue, decreased appetite, and abdominal pain, decreased

calcium, increased ALT, and decreased glucose. Frequent grade 3-4 adverse reactions were diarrhea/colitis, hypertension and hypertensive crisis, QT prolongation, fatigue, and rash. Adverse reactions resulting in death in patients receiving vandetanib (n=5) were respiratory failure, respiratory arrest, aspiration pneumonia, cardiac failure with arrhythmia, and sepsis. In addition, two deaths in patients receiving vandetanib (one sudden death and one death from cardiopulmonary arrest) were noted after data cut-off. QT prolongation, torsades de pointes, and sudden death are included in a boxed warning. Due to the toxicity profile of this agent, a mandatory Risk Evaluation Mitigation Strategy Program and a restricted distribution program was required at the time of its approval in April 2011. While this is a great therapeutic advancement in this patient population, the adverse event profile of this agent makes it unsuitable for a significant number of patients either with slowly progressive disease, limited symptoms or preexisting cardiac disorder. More effective and better tolerated agents will be needed for this patient group.

As characteristic of other endocrine tumors, somatostatin receptor expression has been demonstrated in various histologic types of thyroid cancer.¹¹⁻¹³ While the role of somatostatin receptor signaling in regulating hormone secretion has been well established, it is only more recently that its important role as an endogenous inhibitor of cellular proliferation and activator of apoptosis is becoming recognized. This antiproliferative effect of somatostatin receptor activation has been shown to be both a direct effect as well as off target result of its activation of phosphotyrosine phosphatases that subsequently inhibit the activity of non-somatostatin receptors such as the Insulin-like Growth Factor (IGF) and Epidermal Growth Factor (EGF) Receptors, which play key role in cellular proliferation and survival. Tyrosine phosphorylation of endogenous proteins such as ERK and Akt induced by the somatostatin isoform, SS-14, was clearly shown to result in inhibition of growth hormone and IGF1 mRNA expression.¹⁴ In addition, somatostatin receptor activation using octreotide, potently disrupts downstream signaling through the phosphatidylinositol 3 (PI3) kinase and the mitogen activated protein kinase (MAPK) pathways.¹⁵ Particularly important is the inhibition of PI3 kinase activity due to the dissociation and dephosphorylation of its p85 subunit following somatostatin receptor 2 activation. It is clear from the preceding summary that preclinical studies have provided substantial evidence linking somatostatin receptor inhibitory activity on cellular proliferation to its modulation of the PI3 kinase/Akt/mTOR pathway.

Thyroid stimulating hormone is the key driver of proliferation in normal and neoplastic thyroid epithelial cells. This effect is mediated by convergence of signaling on the AKT/mTOR pathway.¹⁶ Indeed, upstream stimulation of mTOR signaling induced by PTEN haploinsufficiency in mice harboring a dominant-negative mutant thyroid hormone receptor beta (TRbeta(PV/PV) mice) significantly increased the rate of progression of spontaneously formed thyroid tumor and occurrence of lung metastasis leading to reduced survival as compared with PTEN haplosufficient TRbeta(PV/PV)Pten(+/+) mice.¹⁷ Furthermore, a potent and specific inhibitor of the PI3 kinase signaling, LY294002, inhibited downstream mTOR signaling and resulted in reduced thyroid tumor growth and metastasis.¹⁸ The available preclinical evidence demonstrating the important roles of somatostatin receptor and mTOR pathway signaling in thyroid cancer development and progression provides a justification and

a strong rationale for a systematic evaluation of agents targeting these pathways in patients with thyroid cancer. We therefore propose to evaluate the efficacy of everolimus, pasireotide and their combinations in patients with radioiodine refractory thyroid cancers.

1.2 Somatostatin analogs in the treatment of patients with thyroid cancer

There is to date no published report of a prospective trial evaluating somatostatin analogue therapy in thyroid cancer. There is, however, a limited number of case series and case reports showing a variable outcome when patients with radiorefractory or medullary thyroid cancer were treated with somatostatin analogue.

Robbins et al. reported the result in two patients with progressive metastatic papillary thyroid cancer no longer responsive to high doses of ^{131}I or showing lack of uptake on ^{131}I scintigraphy. Pretreatment ^{111}In -pentetreotide scans confirmed the expression of somatostatin receptors by the metastatic deposits. Following approximately 4 months of therapy with long acting octreotide (Sandostatin LAR Depot) therapy, significant reduction was observed in tumor volume and standard uptake values between baseline and restaging ^{18}F -FDG-PET scans.¹⁹

A case series of 8 patients with symptomatic metastatic medullary thyroid carcinoma treated with short acting octreotide in combination with recombinant interferon alpha-2b was reported by Lupoli et al. Octreotide was given at a single daily dose of 150 micrograms for 6 months followed by a daily dose of 300 micrograms for an additional 6 months. Interferon was administered at a dose of 5,000,000 IU intramuscularly 3 times a week for 12 months. Two patients discontinued therapy due to treatment associated toxicities. Although no anatomic response was observed in the tumor deposits, there was symptomatic improvement in five patients. Biochemical response was recorded with significant reduction in serum calcitonin and carcinoembryonic antigen levels within 3 months of starting treatment.²⁰

Long acting octreotide therapy was also shown to be associated with durable biochemical response lasting up to 17 months in three patients with metastatic medullary thyroid carcinoma, two of whom had MEN IIa syndrome. Similar to the case series by Lupoli et al. maximal biochemical response was achieved within 3 months with maximal percent decrease in mean serum calcitonin of 47, 52 and 81% compared to basal values and 45, 60 and 63% in carcinoembryonic antigen (CEA) levels. Response was not durable in the patient with the sporadic form of disease and anatomic correlate of the biochemical response was not reported.²¹

Lanreotide is a cyclic octapeptide somatostatin analogue with affinity for type 2 and type 5 somatostatin receptor subtypes. Vitale et al. combined the long acting form of this agent with recombinant interferon alpha-2b in seven patients with medullary thyroid carcinoma. There

was symptomatic improvement in nearly all patients with associated biochemical response while 5 out of 7 patients achieved disease stabilization.²²

The use of somatostatin analogue therapy for poorly differentiated follicular or papillary thyroid showed poor disease control in part because toxicity limited prolonged treatment. In a series of twelve patients with somatostatin receptor expression confirmed by scintigraphy, only three patients were able to tolerate long term treatment lasting one year or more. All three showed disease progression on FDG PET scan.²³

Overall, experience with somatostatin analogue therapy in thyroid cancer is limited. Available published data suggest that this class of drugs have some efficacy in well differentiated thyroid cancer but little or no anticancer activity in poorly differentiated or anaplastic tumors.

1.3 Pasireotide (SOM230)

Pasireotide is an injectable somatostatin analogue. It is a novel cyclohexapeptide with the following chemical name: (2-Aminoethyl)carbamic acid (2R,5S,8S,11S,14R,17S,19aS)-11-(4-aminobutyl)-5-benzyl-8-(4-benzyloxybenzyl)-14-(1H-indol-3-ylmethyl)-4,7,10,13,16,19-hexa-oxo-17-phenyloctadecahydro-3a,6,9,12,15,18-hexaazacyclopentacyclooctadecen-2-yl ester, di[(S)-2-aminosuccinic acid] salt.

Like natural somatostatin and other somatostatin analogues (SRIFa), pasireotide exerts its pharmacological activity via binding to somatostatin receptors (sst). There are five known somatostatin receptors: sst 1, 2, 3, 4 and 5. Somatostatin receptors are expressed in different tissues under normal physiological conditions. Somatostatin analogues activate these receptors with different potencies²⁴ and this activation results in a reduced cellular activity and inhibition of hormone secretion. Somatostatin receptors are strongly expressed in many solid tumors, especially in neuroendocrine tumors where hormones are excessively secreted e.g. acromegaly,²⁵ GEP/NET²⁶ and Cushing's disease.²⁷

[figure not shown]
The somatostatin analogues currently approved for clinical use (octreotide and lanreotide) have a high affinity to sst subtype 2 (sst2), with moderate or no affinity to the remaining subtypes. Pasireotide is a novel cyclohexapeptide somatostatin analogue that exhibits a unique binding profile, binding with high affinity to four of the five known human somatostatin receptors. (Table 1-1) Compared to Sandostatin[®] (octreotide acetate), pasireotide exhibits a binding affinity which is 30-40 times higher for human sst1 and sst5, 5 times higher for human sst3, and similar to the affinity for sst2 receptors. A detailed summary of available preclinical data is provided in the [\[Investigator's Brochure\]](#).

Table 1-1 Binding profile for octreotide and pasireotide at hsst1-5 (IC₅₀, M)

Compound	sst 1	sst2	sst3	sst4	sst5
octreotide acetate (SMS)	2.8x10 ⁻⁷	3.8x10 ⁻¹⁰	7.1x10 ⁻⁹	>10 ⁻⁶	6.3x10 ⁻⁹
Pasireotide (SOM230)	9.3x10 ⁻⁹	1.0x10 ⁻⁹	1.5x10 ⁻⁹	>10 ⁻⁶	1.6x10 ⁻¹⁰
Ratio of IC ₅₀ : octreotide/pasireotide	30	0.4	5	--	40

Chemical name

Chemical name: (2-Aminoethyl)carbamic acid (2R,5S,8S,11S,14R,17S,19aS)-11-(4-aminobutyl)-5-benzyl-8-(4-benzyloxybenzyl)-14-(1H-indol-3-ylmethyl)-4,7,10,13,16,19-hexaoxo-17-phenyloctadecahydro-3a,6,9,12,15,18-hexaazacyclopentacyclooctadecen-2-yl ester, di[(S)-2-aminosuccinic acid] salt

Chemical structure**Mechanism of action**

SOM230 is a novel cyclohexapeptide somatostatin analogue that exhibits a unique binding profile with high affinity to four of the five known human somatostatin receptors. As compared to Sandostatin[®], SOM230 exhibits a binding affinity, which is 30-40 times higher for human sst1 and sst5, 5 times higher for human sst3, and 2.5 times lower for human sst2. In preclinical experiments, SOM230 showed, in comparison to Sandostatin[®], a more pronounced IGF-1 suppression in four species and a longer biological presence leading to slower elimination.

Human experience

Pasireotide s.c.

Pasireotide when given subcutaneously (s.c.) was well-tolerated at doses up to 600 µg b.i.d., 900 µg b.i.d. and 1200 µg b.i.d. by acromegalic, Cushing's disease and carcinoid tumor patients, respectively. For all indications the most frequently reported adverse events were gastrointestinal, predominantly diarrhea, nausea and abdominal pain. Generally these events were mild, transient and only occasionally caused patients to discontinue treatment.

Hyperglycemia was also observed for some patients in the different indications. When hyperglycemia occurred, it was most common in patients with impaired fasting glucose or diabetes mellitus at baseline. However hyperglycemia in these patients was responsive to appropriate diabetic management such as adjustments in oral antidiabetic treatment, or in some cases the addition of insulin. Occasionally laboratory abnormalities in liver function tests and pancreatic enzymes have been observed at higher doses of pasireotide. These events however have been transient.

Overall the safety profile of pasireotide is comparable to that of currently available somatostatin analogues. However as pasireotide has a broader binding profile (binds to 4 of the 5 sst), and thus more closely resembles natural somatostatin, it may impact secretion of hormones by the pancreas, pituitary, thyroid, adrenals and the gastrointestinal tract. Hence parameters of glucose metabolism (fasting blood glucose, HbA1C), pituitary function (GH, IGF-1, prolactin, ACTH), thyroid function (free T4, TSH) and the adrenals (serum cortisol) will be monitored in this study.

Preliminary safety data are available from a Phase II study [[CSOM230B2202](#)] in 45 patients with symptomatic metastatic carcinoid disease inadequately controlled by octreotide LAR who received pasireotide s.c. doses from 300 µg s.c. b.i.d. up to 1200 µg b.i.d. for a mean of 20 weeks. Pasireotide s.c. has been found to be generally well-tolerated by these patients, with the most common adverse events being mild diarrhea, nausea and abdominal pain. Blood glucose increases occurred in some patients, particularly in those with preexisting DM or impaired fasting glucose, but were moderate and manageable by adjustment in oral hypoglycemic medications in most cases. Weight loss was also observed in 18 patients. Maximum weight loss occurred within 4 to 6 months on the study drug, with a stabilization of effect after approximately 6 months. There was no apparent relationship between the weight loss and pasireotide dose.

Preliminary efficacy data from this study also supports that pasireotide is active in patients refractory/resistant to Sandostatin LAR, as partial or complete symptom control was observed in 12 of 44 patients (27%). Complete response was achieved in two patients at the pasireotide 600 µg s.c. b.i.d. dose and one patient at the 900 µg s.c. b.i.d. dose. Nine patients achieved partial response to treatment, three at each of the following doses: 600, 750, and 900 µg s.c. b.i.d.

The mean pasireotide plasma concentration versus time profiles are shown in [Figure 1-1](#). The mean PK parameters of C_{\min} , C_{\max} and AUC_{0-6hr} for pasireotide are listed in [Table 1-2](#). Since there is no biomarker available for clinical response in carcinoid patients and since clinical response was observed with similar frequency at doses of 600 to 900 μ g s.c. b.i.d., the target pasireotide concentration for symptom control was estimated as approximately 10 ng/mL from the mean C_{\min} value at these doses ([Table 1-2](#)), assuming that a constant drug level is required for pharmacological activity.

[figure not shown]
Further details on pasireotide s.c. can be found in the [\[Pasireotide s.c. Investigator's Brochure\]](#).

Table 1-2 Pasireotide s.c.: Number (%) of patients with most frequent AEs (greater than or equal to 8% for any dose group) regardless of relationship to study drug [CSOM230B2202]

Adverse event (preferred term)	Pasireotide sc						
	300- ≤600µg (N=45) n (CTC≥ grade3)	>600- ≤900µg (N=39) n (CTC≥ grade3)	>900- ≤1200µg (N=42) n (CTC≥ grade3)	>1200- ≤1500µg (N=35) n (CTC≥ grade3)	>1500- ≤1800µg (N=31) n (CTC≥ grade3)	>1800- ≤2400µg (N=10) n (CTC≥ grade3)	Any dose (N=45) n (%) n (CTC≥ grade3)
Weight decreased	6	1	5	1	5	1	19 (42.2)
Abdominal pain	6 (2)	3	4	4	2	0	15 (33.3) (2)
Nausea	6 (1)	2	5	2	3 (1)	0	13 (28.9) (1)
Fatigue	4	1	1	1	6	0	12 (26.7)
Diarrhea	1	1	3 (1)	1	6 (2)	0	11 (24.4) (3)
Hyperglycemia	1	1	0	2 (2)	2 (1)	1	7 (15.6) (3)
Peripheral edema	1	0	1	2	3	0	7 (15.6)
Flatulence	2	1	1	2	1	0	5 (11.1)
Diabetes mellitus	1	0	0	2 (1)	0	1	4 (8.9) (1)
Vertigo	1	2	0	0	1	0	4 (8.9)
Dizziness	2	1	0	1	0	0	4 (8.9)
Vomiting	2 (1)	1	2	0	2 (1)	0	4 (8.9) (1)
Dysgeusia	0	1	0	1	2	0	4 (8.9)
Nasopharyngitis	0	1	1	1	1	0	4 (8.9)
Dyspnea	1	1	2 (1)	0	1	0	4 (8.9) (1)
Hypokalemia	1	1	1	0	0	1	4 (8.9)
Arthralgia	0	0	2	0	2	0	4 (8.9)

Source: [CSOM230B2202]

Figure 1 Error! No text of specified style in document.-1 **Mean (SD) plasma concentration versus time profiles of pasireotide in carcinoid patients (N=26) at week 4 following b.i.d. doses of pasireotide s.c. [CSOM230B2202]**

Source: [CSOM230B2202]

Table 1-3 **Mean (SD) pharmacokinetic parameters of pasireotide in carcinoid patients (N=26) following s.c. b.i.d. doses of pasireotide [CSOM230B2202]**

Dose (s.c.)	C _{min} (ng/mL)	C _{max} (ng/mL)	AUC _(0-6hr) (ng·hr/mL)
150 □g bid (N=1)	1.4	4.7	14.8
450 □g bid (N=4)	5.1 (1.6)	15.2 (3.9)	58.5 (9.5)
600 □g bid (N=6)	10.7 (7.2)	27.9 (12.6)	108 (56.8)
750 □g bid (N=7)	10.5 (4.1)	32.5 (10.2)	130 (37.1)
900 □g bid (N=7)	13.9 (9.2)	32.4 (12.5)	124 (49.7)
1200 □g bid (N=1)	23.3	73.8	271

Source: [CSOM230B2202]

Pasireotide long acting release formulation

Pasireotide LAR in healthy volunteers

Preliminary data from a healthy volunteer [study CSOMC2101] which assessed single i.m. doses of pasireotide LAR up to 60 mg (N=5 per cohort) show that pasireotide LAR was well-tolerated, and that the adverse events observed are comparable with those observed with octreotide LAR. Diarrhea was the most common adverse event which was sometimes associated with abdominal

pain and/or flatulence. The gastrointestinal events were mild or moderate in severity. About half of the subjects reported transient mild injection site pain. Two volunteers on the 60 mg dose had mild increases in fasting blood glucose (< 123 mg/dL) with all values returning to normal within 28 days after the LAR injection.

The exposure of pasireotide was dose-proportional with C_{max} of the extended release phase as 9.6 ± 5.1 ng/mL and 15.8 ± 3.3 ng/mL for 40 mg and 60 mg doses, respectively. Multiple dose simulation suggested that this LAR formulation is suitable for monthly (q 28 d) dosing. The simulated trough concentrations ($C_{trough,ss}$) at steady state were 5.5 and 11.5 ng/mL for the 40 and 60 mg doses, respectively.

Further details on the safety and PK of pasireotide LAR in healthy volunteers can be found in the [\[Pasireotide LAR Investigators' Brochure\]](#).

Pasireotide LAR in carcinoid patients

Safety

Preliminary safety data are available from 20 carcinoid patients inadequately controlled by somatostatin analogues treated with pasireotide LAR in an ongoing study [\[CSOM230C2110\]](#) (Table 1-4). These patients were under treatment with pasireotide LAR i.m. depot injections at doses of 20 mg, 40 mg or 60 mg for up to six weeks at the time of the safety summary. Pasireotide LAR was generally well-tolerated. The most commonly reported AEs were gastrointestinal, however, most of these events were considered unrelated to study drug.

Table 1-4 Pasireotide LAR: Number (%) of patients with most frequent AEs (> 5% for any dose group) regardless of relationship to study drug (preliminary data from study SOM230C2110)

[figure not shown]
Adverse Event (Preferred term)	Pasireotide LAR 20mg (N=5) n (CTC= grade3)	Pasireotide LAR 40mg (N=7) n (CTC= grade3)	Pasireotide LAR 60mg (N=8) n (CTC= grade3)	Pasireotide LAR Any dose (N=20)n (%) (n=CTC grade3)
Diarrhea	1	2	2	5 (25.0%)
Fatigue	1	2 (1)	1	4(20.0%) (1)
Dyspnea	1	2 (1)	1	4 (20.0%) (1)
Flushing	1	1 (1)	1 (1)	3 (15.0%) (2)
Back Pain	1	1	1	3 (15.0%)
Nausea	1	1	0	2 (10.0%)
Palpitations	0	2	0	2 (10.0%)
Abdominal Pain	1	1	0	2 (10.0%)
Steatorrhea	1	1	0	2 (10.0%)
Asthenia	1	1	0	2 (10.0%)
Headache	0	1	1	2 (10.0%)
Anorexia	0	1	1	2 (10.0%)
Hyperglycemia	0	1 (1)	1	2 (10.0%) (1)
Odema Peripheral	0	1	0	1 (5.0%)
Erythema	1	0	0	1 (5.0%)

Source: [\[SOM230C2110\]](#)

Pharmacokinetics

Interim PK analysis has shown that a steady state appeared to be achieved following three monthly i.m. injections of 20 mg (N=5), 40 mg (N=7) or 60 mg (N=8) pasireotide LAR in carcinoid patients. The mean (SD) concentration versus time profiles of pasireotide are shown in [Figure 1-2](#). The median (mean \pm SD) trough plasma concentrations of pasireotide on days 28, 56 and 84 are shown in [Table 1-3](#). The release pattern of pasireotide from the first injection of 40 and 60 mg LAR in carcinoid patients ([Figure 1-2](#)) was very similar to that of a single-dose of 40 and 60 mg LAR in healthy volunteers. PK exposures to pasireotide on day 84 at steady state in carcinoid patients ([Table 1-3](#)) were roughly 2-fold higher than the simulated concentrations at steady state following multiple doses in healthy volunteers ([Section 1.3.2.1](#)).

Figure 1 Error! No text of specified style in document.-2 **Mean (SD) plasma concentration versus time profiles of pasireotide in carcinoid patients following three monthly i.m. injections of 20 mg (N=5), 40 mg (N=7), or 60 mg (N=8) pasireotide LAR [CSOM230C2110]**

Source: [SOM230C2110]

Table 1-5 **Median (Mean plus or minus SD) trough plasma concentrations of pasireotide on days 28, 56 and 84 in carcinoid patients following three monthly i.m. injections of 20 mg (N=5), 40 mg (N=7) or 60 mg (N=8) pasireotide LAR [CSOM230C2110]**

Dose (mg)	Day 28 (ng/mL)	Day 56 (ng/mL)	Day 84 (ng/mL)
20 (N=5)	2.7 (N=2)	5.7 (N=1)	6.9 (N=1)
40 (N=7)	7.2 (10.6 ± 8.2) (N=6)	5.9 (13.8 ± 16.8) (N=3)	12.0 (17.7 ± 10.5) (N=3)
60 (N=8)	14.2 (15.6 ± 9.2) (N=8)	28.2 (28.5 ± 7.8) (N=4)	16.9 (16.2 ± 4.8) (N=4)

Source: [SOM230C2110]

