6.9 Study drug discontinuation

Patients experiencing unacceptable toxicity (AE grade 3 or higher) that the investigator considers directly attributable to the study drug should have their dose adjusted as per dose modification guidelines in Table 6-2. If a patient has already decreased 2 dose levels, no further dose reduction is permitted, and the patient will be permanently discontinued from treatment. A delay of more than 21 days in resuming study drug due to treatment-emergent adverse event will result in the withdrawal of the patient from the study (non-treatment related delay of more than 21 days but no more than 28 consecutive days may be allowed to resume therapy after discussion with the overall PI). Patient so withdrawn should undergo the required end of study procedures follow-up post treatment discontinuation.

Premature patient withdrawal/End of treatment

Patients **may** voluntarily withdraw from the study or be dropped from it at the discretion of the investigator at any time. Patients may be withdrawn from the study if any of the following occur:

- Disease progression or lack of efficacy
- Uncontrolled diabetes mellitus (DM)
- Pregnancy
- Adverse event(s)
- Abnormal laboratory value(s)
- Abnormal test procedure result(s)

QT-related discontinuation criteria

- Confirmed QTcF >480msec and discontinuation recommended by a cardiologist
- New occurrence of clinically significant/symptomatic bradycardia
- Increased risk of QT prolongation by use of QT prolonging medication
- Hypokalemia (<3.5 mmol/L) or hypomagnesaemia (<0.7 mmol/L) confirmed by repeat testing that is either a new finding or accompanied by vomiting or diarrhea and not corrected by treatment
- Protocol violation
- Subject withdrew consent
- Lost to follow-up
- Administrative problems
- Death
- Disease progression
- Treatment duration completed as per protocol

7 Visit schedule and assessments

Table 7-1 lists all of the assessments and indicates the visits at which they are to be performed with an “X”. All data obtained from these assessments must be supported in the patient’s source documentation. To accommodate scheduling challenges, the required assessments may be performed within +/- 2 days of the specified scheduled dates.

Hepatitis Screening

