Inclusion and exclusion criteria	X												
Diagnosis and stage of cancer	X												
Prior and ongoing therapy	X ^a												X
Randomization	X												
Physical exam	X	X		X		X		X	X	X	X [#]	X	
Vital signs	X	X	X	X		X	X	X	X	X	X [#]	X	
ECG	X [*]	X	X [*]				X [*]			X [*]			
Gallbladder ultrasound	X ^b												
Performance Status	X	X		X		X		X	X	X	X [#]	X	
Hematology	X	X ^{&}		X		X		X	X	X	X [#]	X	
Glycosylated hemoglobin	X ^c	X ^{&}											
PT, PTT	X	X ^{&}											
CMP including fasting cholesterol and triglyceride [@]	X	X ^{&}		X		X		X	X	X	X [#]	X	

Table 7-1 Schedule of Events and Assessments

Patient assessments and the visits at which they are to be performed are indicated with an “X”. All data obtained from these assessments must be supported in the patient’s source documentation.

In order to accommodate scheduling challenges, the required assessments may be performed within +/- 2 days of the specified scheduled dates.

Examination	Screening/ Baseline		Pasireotide i.m. Everolimus p.o								End of Study	Follow-up	
LFT assessment ⁺	X	X	X	X	X	X		X	X	X	X [#]	X	
Hepatitis screening	X [%]												
Tumor Markers: Medullary: Free T4, TSH, CEA, Calcitonin and chromogranin A; Differentiated: TSH, free T4, thyroglobulin, thyroglobulin antibodies.	X					X			X		X [#]		
Biomarker Samples (IGF-1, optional PBMC)	X ^d					X			X		X		
Urinalysis	X	X ^{&}											
Pregnancy test	X	X ^{&}											
Archival tissue collection	X ^e												
MRI/CT Scan	X ^f					X			X		X		
Study Drug Administration		X		X		X		X	X	X	X		
Response Assessment						X			X		X		
Adverse events	X	X		X		X		X	X	X	X	X	X
Concomitant medications	X	X		X		X		X	X	X	X	X	

^s cycle 7 and beyond

& need not be repeated if within normal institutional reference limits and obtained within 7 days of C1D1

@ Albumin, alkaline phosphatase, total bilirubin, calcium, chloride, creatinine, magnesium, potassium, total protein, SGOT, SGPT, sodium, bicarbonate, total protein, total cholesterol, LDL cholesterol, HDL cholesterol, triglycerides, urea/BUN γ -GT, fasting blood glucose, phosphorous, [at screening and as clinically indicated: CPK, HbA1c, LDH lipase, α -amylase and uric acid]. If the total bilirubin concentration is increased above 1.5 times the upper normal limit (UNL), total bilirubin should be differentiated into the direct and indirect reacting bilirubin (patient may be treated if direct bilirubin is $< 1.5 \times$ UNL)

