c: repeat as necessary if patient is a known diabetic or if baseline values elevated

d: obtain peripheral blood sample for IGF-1 at the end of every even number cycle (up to end of cycle 6) as part of restaging evaluation

e: if archival tissue cannot be obtained, upto-20 unstained slides may be collected if available.

f: same modality should be used for each restaging; other imaging studies may be obtained in addition as necessary for clinical management. **Baseline scan must be obtained not later 30 days of initiation of drug administration.**

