7.5 Safety

Safety assessments will consist of monitoring and recording all adverse events and serious adverse events, the regular monitoring of hematology, blood chemistry and urine values, regular measurement of vital signs and the performance of physical examinations.

These assessments should be performed within ± 2 days of the scheduled day of assessment except for adverse events that will be evaluated continuously through the study. Safety and tolerability will be assessed according to the NIH/NCI CTCAE version 4.0 http://ctep.cancer.gov/protocolDevelopment/electronic_applications/docs/ctcae4.pdf.

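### Section 1.3 commits the study to monitoring nine endocrine and metabolic parameters, but the schedule covers five: GH, prolactin, ACTH and serum cortisol are not scheduled, so neither adrenal-axis test is planned

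*Combined protocol and SAP*

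**What the plan says.** Section 1.3 (Human experience, under the subcutaneous pasireotide subheading) notes the drug's broad receptor binding and says that "it may impact secretion of hormones by the pancreas, pituitary, thyroid, adrenals and the gastrointestinal tract". It draws a consequence: "Hence parameters of glucose metabolism (fasting blood glucose, HbA1C" opens a list that continues "pituitary function (GH, IGF-1, prolactin, ACTH), thyroid function (free T4, TSH) and the adrenals (serum cortisol) will be monitored in this study". The same paragraph says "Overall the safety profile of pasireotide is comparable to that of currently available somatostatin analogues".

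Section 7 states that "Table 7-1 lists all of the assessments and indicates the visits at which they are to be performed". In that table the thyroid tests sit in the marker row: "Tumor Markers: Medullary: Free T4, TSH, CEA, Calcitonin and chromogranin A; Differentiated: TSH, free T4, thyroglobulin, thyroglobulin antibodies". HbA1c is marked at screening and C1D1, with a footnote to "repeat as necessary if patient is a known diabetic or if baseline values elevated". IGF-1 is in the biomarker row. Section 7.5.4.1 covers free T4 and TSH, and Section 7.5.4.2, on hormones, names IGF-1 alone.

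Besides recording adverse events, Section 7.5 describes safety assessment as "the regular monitoring of hematology, blood chemistry and urine values, regular measurement of vital signs and the performance of physical examinations".

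**The concern.** The commitment in Section 1.3 is specific. It names the tests, gives a pharmacological reason and refers to this study, which gives only the long-acting formulation. Other pasireotide risks have their own schedules: ECGs, liver tests and glucose monitoring (Section 6.7 and Table 7-1). The pituitary and adrenal part was only partly carried through, and no section says why.

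What is at stake is a precaution that the protocol sets itself. A site that follows Table 7-1 will not draw cortisol or ACTH. Without a baseline value, a test ordered later because of symptoms has nothing to be compared with. Obtaining more safety data on concurrent and sequential dosing is a secondary objective (Section 3.2), so the gap bears on something that the trial set out to learn.

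**Working it through.** The plan gives no figure to reproduce. The check is a cross-tabulation of the parameters in Section 1.3 against the schedule, followed by counts of patients and assays.

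**Step 1. Parameters promised and scheduled**

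| Parameter (Section 1.3) | Table 7-1 | Section 7.5.4 |
|---|---|---|
| Fasting glucose | Chemistry row, each cycle to C6, then every other cycle | Listed |
| HbA1c | Screening and C1D1; later only if diabetic or elevated at baseline | Screening and as clinically indicated |
| IGF-1 | Screening, C3D1, C5D1, C7D1 (to end of cycle 6) | 7.5.4.2 |
| Free T4 | Marker row, screening and restaging visits | 7.5.4.1 |
| TSH | Marker row, screening and restaging visits | 7.5.4.1 |
| GH | None | None |
| Prolactin | None | None |
| ACTH | None | None |
| Serum cortisol | None | None |

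Section 7.7 and Appendix B (biomarker samples) name no hormone other than IGF-1.

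- Promised: 2 glucose + 4 pituitary + 2 thyroid + 1 adrenal = 9.
- Scheduled: 5. This is a generous count, because HbA1c repeats are conditional and IGF-1 stops after cycle 6.
- Not scheduled: 9 − 5 = 4, and 4/9 = 44%.
- Adrenal-axis tests named (ACTH, cortisol): 2, of which 0 are scheduled.

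**Step 2. Patients concerned**

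- Lower end, if Arms B and C both close after stage I: 2 × 18 = 36 evaluable. Section 7.4 expects about 5% of patients to be inevaluable, and 36/0.95 = 37.9, about 38. That assumes the inevaluable patients received drug. The 5% covers safety as well as efficacy, and any dose makes a patient safety-evaluable, so some of them may have received none. The range is 36 to 38.
- Full planned enrolment (Section 5): 2 × 30 = 60.
- Arm A patients who cross over to A1: 0 to 30 more.

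**Step 3. Assays if cortisol is added**

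- To week 24 (6 cycles × 4 weeks): baseline, C1D22, C3D1, C5D1, C7D1 = 5 per patient.
- To week 48 (12 cycles × 4 weeks): add C9D1, C11D1, C13D1 = 8 per patient.
- Arms B and C at full enrolment, nobody stopping early: 60 × 5 = 300 and 60 × 8 = 480.
- A1, if all 30 cross over: 30 × 5 = 150 and 30 × 8 = 240 more.
- Repeats: the documents give no rate of low values. If 2.5% to 10% were low (an assumption), Arms B and C would need 300 × 0.025 = 7.5 (about 8) repeats at the low end and 480 × 0.10 = 48 at the high end.

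The week-48 count matters because Section 4 cites a median PFS of 9 to 18 months for targeted agents in similar patients, so treatment past week 24 is foreseeable.

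**The case against.** The strongest reply is that this is one introductory sentence out of step with an operative schedule that agrees with itself. Table 7-1 and Sections 7.5.4.1 and 7.5.4.2 do not conflict, so a site working from them meets no contradictory instruction. Section 1.3 says only that secretion may be affected. The adverse event tables for both formulations list no adrenal or pituitary event, though they show only frequent events. Amending Section 1.3 would restore consistency without a single new assay.

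Much of this stands, and it is why the severity is low. Two things remain. The schedule is consistent only because it leaves out what Section 1.3 commits to. And deleting cortisol from Section 1.3 would settle the wording while withdrawing the precaution, with the stated reason for it left unanswered.

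A reader might infer that adrenal tests are not done at all, or that adrenal function goes wholly unwatched. The documents do not support that. The tests are not scheduled, but an investigator may order one when clinically indicated. Sodium, potassium, bicarbonate and fasting glucose are in the routine chemistry panel, weight and supine blood pressure are taken as vital signs (Section 7.5.2), and adverse events are sought at each visit (Section 7.5.1). These checks are indirect and non-specific. Weight loss (42.2%), nausea (28.9%) and fatigue (26.7%) were already common on subcutaneous pasireotide (Table 1-2).

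A reader might also infer that patients are being harmed or that the trial's conclusions are in doubt. No adrenal event is reported, and Section 1.3 calls the overall profile comparable to that of existing analogues. Response rate, PFS and the two-stage rule do not use these hormones. Safety enters the choice of winning arm only as the last tie-break, which names no laboratory test.

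**Conclusion.** The inconsistency is real and of low severity. Four of the nine parameters that Section 1.3 says will be monitored have no scheduled measurement, and these include both adrenal-axis tests it names. The gap concerns 36 to 60 patients in Arms B and C, depending on whether the arms pass stage I, and up to 30 more in A1. Those numbers measure exposure to an unscheduled precaution; they are not an estimate of harm.

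The conclusion rests on taking Section 7 at its word that Table 7-1 is complete, and on reading the commitment in Section 1.3 as applying to this trial, as it says. The text between Sections 7.5.1.3 and 7.5.2 and the attached monitoring-plan supplement were not available for this check. The former lies outside the laboratory sections and the visit table, so it is unlikely to change the result.

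**What to change.** For patients receiving pasireotide (Arms B and C, and A1 starting before its first injection), amend Table 7-1 and Section 7.5.4.2 as follows.

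- **Sampling.** Add a locally read morning serum cortisol at baseline, at C1D22, at C3D1, C5D1 and C7D1, and then every other cycle while on pasireotide. C1D22 is already a blood draw for liver tests, and Section 6.7 treats day 21 as the peak-concentration visit, so it gives an early on-drug value.
- **Steroids.** Record corticosteroid use with each sample and treat values taken on steroids as not interpretable. Chronic systemic steroids are excluded at entry, but Table 6-5 and Section 6.8 allow some use on study.
- **Action.** In a patient not on steroids, repeat a low value by the next injection visit. If it is confirmed, the investigator reviews it before the next dose, with endocrine evaluation as indicated. The adverse event rule in Section 7.5.1 is not enough alone, because an asymptomatic low value might trigger nothing.
- **Other analytes.** Schedule ACTH, prolactin and GH likewise, or remove them from Section 1.3 with a reason.

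The cost is the cortisol assays counted above: about five per patient to week 24 and eight to week 48, with A1 and repeats on top. No extra scheduled visit is needed, because fasted, early-day, locally analysed samples are already the rule in Section 7.5.4. A repeat may occasionally need an extra draw. If ACTH and GH are kept, sample handling should be checked with the local laboratories. Adding or deleting a required safety test needs a protocol amendment with IRB approval (Section 10.3).
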